Official Title: Effects of Toe-out Gait Modification on Clinical and Biomechanical Measures in People with Knee Osteoarthritis

- NCT Number: NCT02019108
- **Document Date:** November 25, 2013

Methods

Participants

Community-dwelling individuals were recruited via an existing laboratory database as well as advertisements in print media. Inclusion criteria were: (i) definitive medial tibiofemoral osteophytes on x-ray; (ii) joint space narrowing greater in the medial tibiofemoral compartment compared to the lateral compartment; (iii) history of knee pain longer than six months; and (iv) average knee pain of at least 3 out of 10 over the one month period prior to initial screening. Exclusion criteria were: (i) knee surgery or intra-articular pain relief injection within six months; (ii) current or past (within six months) oral corticosteroid use; (iii) history of knee joint replacement or tibial osteotomy; (iv) any other condition affecting lower limb function; (v) participation in a new structured exercise program within the past three months, or planning to commence exercise or other treatment for knee OA in the next four months; and, (vi) an inability to travel to the university to attend testing and training sessions. The study was approved by the Institution's Clinical Research Ethics Board and all participants provided written informed consent.

Sample size was determined based on randomization with stratification, and covarying for baseline values in the statistical analysis. Using effect size estimates of 0.8 for WOMAC pain and 1.0 for KAM impulse, based on pilot data using a similar design, it was determined that participants in each group was required to attain 90% power to detect significant differences in pain and KAM outcomes between groups with an alpha of 0.05. Using a conservative estimate of 10% attrition, the aim was to recruit 73 participants for this study.

Study Design

This was a parallel group, assessor-blinded, randomized controlled trial. Interested participants were initially screened for inclusion and exclusion criteria over the telephone and eligible individuals then underwent a physical screen. Screening was overseen by a researcher not involved in data collection or analysis.

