This physical screen was conducted to confirm the presence of knee pain, and to perform a preliminary walking assessment to assess self-selected foot progression angle. Participants performed three trials of self-selected, over ground walking while three reflective skin markers tracked the movement of the sacrum, the second toe, and posterior calcaneus of the study limb (defined as the self-declared osteoarthritic limb in those with unilateral symptoms, or the most painful limb in the case of bilateral symptoms). The mean foot progression angle across the three trials was calculated. As the goal of the toe-out modification program was to increase the self-selected, baseline foot progression angle by 15° in the toe-out direction, 15° of toe-out at the physical screening was selected as the threshold. This was done due to (i) the difficulty in achieving toe-out angles of 30° by people with knee OA, and (ii) the fact that those who already exhibit large amounts of toe-out would likely not be candidates for toe-out gait modification in the clinical setting.

Those who passed physical screening were referred for radiographic evaluation. Standing, semiflexed, postero-anterior radiographs were obtained and graded for disease severity using the Kellgren and Lawrence (KL) OA classification system.

Individuals who met the radiographic criteria listed above were invited to the laboratory for a baseline (Week 0) testing session where self-report questionnaire, objective physical function, and biomechanical data were collected. Following completion of baseline testing, the randomization procedure was conducted by a study biostatistician who was not involved in any aspect of data collection or training. Randomization was initiated by the study research coordinator, who provided the biostatistician with each participant's study ID, sex, and KL grade. The biostatistician then responded via email with the group allocation, and maintained the randomization parameters and list offsite. Group allocations were determined prior to study commencement, and randomization was stratified by sex (male, female) and disease severity (mild or moderate grouped together, severe).

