Participants returned to the university the following week (Week 1) to begin their training program, and were informed of their group allocation at this time. Each home-based program lasted four months and was supplemented with eight training sessions with the study trainer at Weeks 1, 2, 4, 6, 8, 10, 12 and 15 of the intervention, with typical sessions lasting 20 minutes in Week 1 and increasing to 40 minutes by Week 15. All training sessions, regardless of group allocation, were conducted by the same trainer in the same rehabilitation gymnasium. The first training session for each participant was always a one-on-one session with the trainer, with subsequent sessions conducted in groups of one to three individuals; in cases of group sessions, only individuals from the same group allocation were present in the gymnasium to prevent cross-contamination of groups.

Follow-up testing occurred four months after baseline testing, with a final retention testing session conducted one month later. The same outcome measures, completed in the same testing order, and by the same blinded assessor, were collected at each testing session. No training or instructions of any kind were provided between these final two testing sessions.

Interventions

For both groups, the intent was to increase the weekly amount of walking out in the community by 40% over and above that exhibited prior to enrollment. Initial values were assessed via discussion with participants at the first training session, and prescribed weekly increases were determined individually at each training session in consultation with the trainer.

Toe-out (TO) gait modification program

Participants randomized to the TO program were trained to perform walking with 15° more toeout than the self-selected amount measured at the baseline testing session. Our previous pilot study showed modest improvements of 6.7° in self-selected toe-out angle following 10-weeks of toe-out gait retraining intending to increase toe-out by 10°, that resulted in marginally statistically significant improvements in late stance KAM (p=0.04) and self-reported pain (p=0.02), and non-significant decreases in KAM impulse (p=0.20). Thus, a larger toe-out increase was selected for this study.

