Gait data were recorded for barefoot, over ground walking trials at a self-selected speed. Twentytwo retro-reflective markers were affixed to the participant according to a modified Helen Hayes marker set, and their movements were captured using twelve high-speed digital cameras (Motion Analysis Corp., Santa Rosa, CA) sampling at 100 Hz. An initial standing static trial was collected using additional markers placed over the medial malleoli and femoral epicondyles to determine segment orientations and joint centres of rotation. Kinematic data from the cameras were synchronized with two force platforms (OR6-6, Advanced Mechanical Technologies Inc.) visually concealed in the floor of a 10m walkway and sampling data at 2000 Hz. Participants were provided no instructions pertaining to walking mechanics during any of the gait assessments.

Inverse dynamics techniques and commercially available software (Orthotrak, Motion Analysis Corp.) were used to calculate gait variables including: KAM (early stance peak, late stance peak, impulse), peak external knee flexion moment (KFM) during stance, and mean foot progression angle during foot-flat (positive values = toe-in orientation, negative values = toe-out orientation). The mean value from five walking trials was calculated for each biomechanical variable.

Adherence, concurrent treatments, and adverse events during interventions

Adherence to both training programs was assessed as the total number of supervised walking sessions attended for each participant. Compliance with the prescribed walking increases was obtained from log book data completed by participants detailing their daily amount of walking for the duration of the study, and weekly totals (in hours) were calculated. Additionally, an 11-point NRS (0 = "not confident at all", 10 = "very confident") in the log book was used to assess self-reported confidence in the ability of those in the TO group to maintain the increased toe-out angle whilst walking in the community. Finally, concurrent treatments and adverse events reported during the intervention were assessed using open-ended questions in the log book maintained by the participants. For the purposes of analysis, adverse events were defined as those lasting longer than two weeks in duration, or requiring additional treatment.

Statistical analysis

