The primary outcomes were WOMAC pain, KAM impulse, and foot progression angle, and the primary endpoint was the follow-up assessment. All other biomechanical and clinical outcomes were considered secondary in nature. Between-group comparisons were the primary analyses, with within-group comparisons used for informational purposes. Analysis of covariance (ANCOVA) models were fit predicting each outcome variable evaluated at both time points (follow-up and retention), with group as predictor, and while controlling for baseline values. For biomechanical outcomes (knee adduction and flexion moments, as well as foot progression angle), additional models were computed while additionally controlling for concurrent gait speed at the associated time point (follow-up or retention). For baseline data, crude means were computed. Adjusted least squares means (LS means) with standard errors and 95% confidence intervals were computed for each group at both follow-up and retention. Adjusted LS means were computed in similar models for within-group (delta) scores. Finally, model-adjusted group effects were computed, along with p-values and 95% confidence intervals, for all outcomes.

All data were analyzed using an intention-to-treat analysis, and the primary analyses assumed that data were missing completely at random (MCAR). In sensitivity analyses, multiple imputation was performed as per the methods described by van Buuren. Results and conclusions were compared to the MCAR analysis, and any differences noted. All statistical analyses were conducted by a biostatistician blinded to group allocation and who was not involved in any other aspect of the study. Analyses were performed using SAS v9.4 (SAS Institute, Cary, North Carolina).

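### Do the speed-adjusted gait models fail because they adjust for follow-up speed but leave out baseline speed?

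*Combined protocol and SAP*

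**What the plan says.** The Statistical analysis section fits an ANCOVA for every outcome at follow-up and at retention, "with group as predictor, and while controlling for baseline values". These between-group comparisons are the primary analyses. For the knee adduction and flexion moments and foot progression angle it then says that "additional models were computed while additionally controlling for concurrent gait speed at the associated time point (follow-up or retention". No model names baseline gait speed. The section gives no purpose, decision rule or estimand for the speed-adjusted models.

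Baseline speed should be obtainable. Study Design describes a "baseline (Week 0) testing session where self-report questionnaire, objective physical function, and biomechanical data were collected", and adds: "The same outcome measures, completed in the same testing order, and by the same blinded assessor, were collected at each testing session". Under Gait biomechanics, "Gait data were recorded for barefoot, over ground walking trials at a self-selected speed", and "Participants were provided no instructions pertaining to walking mechanics during any of the gait assessments".

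The document gives no mean, SD or visit-to-visit correlation for gait speed, and no expected difference in speed between the arms.

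**The concern.** Speed at testing is chosen by the participant, so the baseline outcome reflects baseline speed and the follow-up outcome reflects follow-up speed. The additional models correct the second and not the first. Randomisation balances baseline speed, but comparing the arms at equal follow-up speed can undo that balance. If training shifts speed in one arm by d, participants matched on follow-up speed differ in baseline speed by d times the correlation of speed between visits. The baseline outcome then carries some of the speed information, the fitted slope on follow-up speed becomes too flat, and part of the speed effect stays in the group coefficient.

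What would be at stake is interpretation. KAM impulse and foot progression angle are two of the three primary outcomes. A reader may take a result that barely moves after speed adjustment as evidence for a toe-out mechanism, although the model could hardly have moved it.

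**Working it through.** **Trial size.** The plan sizes each arm as "required to attain 90% power" to detect "significant differences in pain and KAM outcomes between groups with an alpha of 0.05". With effect size 0.8 (WOMAC pain), two-sided testing and 1:1 allocation (both assumed), n = 2(1.960 + 1.282)²/0.8² = 32.8, so 33 per arm and 66 in total. Adding 10% gives 66 × 1.10 = 72.6, the stated 73; dividing by 0.90 gives 74. The target reproduces. Gait speed plays no part in it, and 33 per arm is used below.

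**Model in which the concern is correct.** All inputs are assumptions. Within-arm SDs at baseline are 1. B is the slope of outcome on speed, r the correlation of speed between visits, c the correlation of the outcome between visits, and d the arm difference in follow-up speed.

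- Slope on follow-up speed given group and baseline outcome: B(1 − rc)/(1 − B²r²).
- Part of the speed effect left in the group coefficient: d × (B − slope).
- With baseline speed added, the slope is B and nothing is left.

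At r = c = 0.8, B = 0.3, d = 0.3, the slope is 0.3 × 0.36/0.9424 = 0.115. The residual is 0.3 × (0.3 − 0.115) = 0.056 SD out of 0.3 × 0.3 = 0.09 SD, or 62%. Over r and c from 0.5 to 0.9 and B from 0.05 to 0.5, the share left runs from 20% (r = c = 0.5, B = 0.5) to 81% (r = c = 0.9, B = 0.05). Simulation agrees. The algebra is sound; what matters is its conditions.

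**Condition 1: the arms differ in speed.** If d = 0 the residual is zero whatever B, r and c are. In simulations with 400,000 participants per scenario and a true effect of −0.50, both models returned −0.50 when d = 0. At N = 66 the standard error was 0.145 under the plan and 0.135 with baseline speed, so only some precision is lost. The Interventions section gives little reason to expect a large d: both groups have a 40% increase in weekly walking as their target, with the same trainer and session schedule, and the comparison arm does the treadmill and mirror training without the toe-out element.

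**Condition 2: speed affects the outcome.** If B = 0 there is no bias. That is possible for foot progression angle.

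**Condition 3: no unmeasured cause of both follow-up speed and outcome.** Pain or conditioning at the visit could be such a cause. Suppose it explains half of the change in speed not predicted by baseline speed, and shifts the outcome by u SD. At r = c = 0.8, B = 0.3, d = 0.3, the unpredicted variance is 1 − 0.64 = 0.36, and the cause enters speed with coefficient √(0.36/2) = 0.424.

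- Slope under the plan: (0.3 + 0.424u − 0.192)/0.9424, where 0.192 = 0.3 × 0.8 × 0.8.
- Slope with baseline speed: 0.3 + 0.424u/0.36.

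| u | Residual, plan (SD) | Residual, baseline speed added (SD) |
|---|---|---|
| 0 | 0.056 | 0.000 |
| +0.1 | 0.042 | −0.035 |
| +0.2 | 0.029 | −0.071 |
| −0.2 | 0.083 | 0.071 |

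The absolute residuals are equal when 1.179u = 0.185 − 0.450u, that is, at u = 0.185/1.629 = 0.11. Above that value the plan is closer to zero in this case.

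The pattern is not confined to one case. With a stronger common cause (coefficient 0.4 on both speed and outcome), r of 0.6–0.8, slopes of 0.3–0.5 and d of ±0.3, the planned model removed about 80–113% of the speed-mediated difference and the expanded model about 147–249%. With a modest common cause (0.1–0.2 SD) and d = 0.3, adding baseline speed came closer to zero in only about half of 96 simulated settings.

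**Practical size, 33 per arm, no common cause, no speed-independent effect.**

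| B | d | Residual (SD) | p < 0.05 under the plan |
|---|---|---|---|
| 0.1 | 0.3 | 0.01–0.02 | 4.9–5.4% |
| 0.3 | 0.3 | 0.02–0.07 | 5.0–10% |
| 0.5 | 0.5 | 0.05–0.19 | 5.4–40% |

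At the planned KAM impulse effect of 1.0, the speed-adjusted test is significant in 97–100% of trials under the plan and 93–100% with baseline speed added.

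**The case for a change.** The best case for changing the plan is that baseline speed costs one degree of freedom of about 62 and needs no new measurement. With no common cause it removes the whole speed effect; at r = c = 0.8, B = 0.3 the planned model removes only 38%. A toe-out gait might itself change self-selected speed, so an arm difference cannot be excluded. When the common cause is habitual speed measured with error, adding baseline speed was closer to full removal in 29 of 36 settings, equal in 2 and further in 5.

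The algebra and the low cost stand, and a statistician who prefers the larger covariate set has a respectable case. Two things do not follow. First, the 29 of 36 depends on the confounder chosen: habitual speed is what baseline speed is a proxy for, whereas a visit-specific cause can reverse the ranking, as shown above. Where the planned model then does better, it is because two biases partly offset; that is no virtue of the model, but it means the larger set cannot be called the correct one. Second, the claim that adjusted and unadjusted results will stay close is not general, since up to 80% of the speed effect is removed within the concern's own range.

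Concurrent speed is also measured after randomisation, and the plan does not say what the speed-adjusted models estimate. That limitation is real. Adding baseline speed leaves it in place.

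**Conclusion.** The omission is a fact, but it is not an error. Partial removal of the speed effect follows only if the arms walk at different speeds at follow-up, speed affects the outcome, and no unmeasured factor drives both. The document supports none of these, and every magnitude rests on assumed inputs. With equal speeds the omission costs some precision (standard error 0.145 against 0.135). With B and d at 0.3 and no common cause, the residual is 0.02–0.07 SD; the extreme of 0.19 SD needs a slope and an arm difference of 0.5 each together with very stable speed and outcome (r = c = 0.9). With a moderate common cause, the proposed covariate may help or harm, and the plan gives no basis for saying which.

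The main ANCOVA contains no speed term, so the primary comparisons and their p-values do not depend on this choice. Both covariate sets give imperfect adjustments for a post-randomisation variable in additional models, and reasonable statisticians could pick either. No change to the plan is needed on this point.

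### Do the extra models that adjust for gait speed at the outcome visit leave the primary result for KAM impulse and foot progression angle undecided?

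*Combined protocol and SAP*

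**What the plan says.** The Statistical analysis section names three primary outcomes (WOMAC pain, KAM impulse and foot progression angle) and makes the follow-up visit the primary endpoint. It fits an ANCOVA to every outcome at follow-up and at retention, "with group as predictor, and while controlling for baseline values". For the knee moments and foot progression angle it then says that "additional models were computed while additionally controlling for concurrent gait speed at the associated time point (follow-up or retention"). It closes the description of the models with "model-adjusted group effects were computed, along with p-values and 95% confidence intervals, for all outcomes".

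Three other places bear on the point:

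- Sample-size paragraph under Participants: "Sample size was determined based on randomization with stratification, and covarying for baseline values in the statistical analysis". Gait speed is not mentioned there.
- Gait biomechanics: walking trials are done at a speed that the participant chooses.
- Study Design: randomisation follows the baseline session, so speed at follow-up and retention is a post-randomisation measurement.

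The same analysis section does label its missing-data approaches. It says that "the primary analyses assumed that data were missing completely at random (MCAR"), calls multiple imputation a sensitivity analysis, and says that differences between the two will be noted. No such label or comparison rule is attached to the speed models.

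**The concern.** Adjusting for something measured after randomisation changes the question. If toe-out training alters walking speed, and speed is related to KAM impulse, a model that holds follow-up speed fixed no longer estimates the total effect of being randomised to toe-out. It estimates something closer to the part of the effect that does not act through speed, and even that only if speed and outcome share no unmeasured cause.

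Two primary outcomes therefore get a second between-group estimate, and possibly a second p-value, with no stated purpose and no rule for disagreement. The statement that between-group comparisons are primary does not separate the two models, because both are between-group comparisons. At stake would be the freedom to base the conclusion on whichever model was significant. That matters most if the true effect is below plan. This is conceivable, since the toe-out programme section reports a non-significant change in KAM impulse in the pilot (p=0.20).

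**Working it through.** **Which model leads, from the text**

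1. Order and wording: the ANCOVA on group and baseline value is given for each outcome. The speed models follow and are called *additional*.
2. Coverage: group effects with p-values are promised for all outcomes. WOMAC pain has no speed model, so the baseline-adjusted ANCOVA is the only model that exists for all of them.
3. Design basis: the sample size rests on stratified randomisation and baseline values.

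All three point to the baseline-adjusted ANCOVA.

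**The plan's own figure**

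Inputs from the sample-size paragraph: "Using effect size estimates of 0.8 for WOMAC pain and 1.0 for KAM impulse", 90% power, alpha 0.05, 10% attrition, 73 to recruit. Two-sided testing and 1:1 allocation are assumed.

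- n per arm = 2 × (1.960 + 1.282)² / d². For d = 0.8 this is 2 × 10.51 / 0.64 = 32.8, so 33 per arm and 66 in total.
- Attrition: 66 / 0.9 = 73.3, or 66 × 1.1 = 72.6. Both agree with 73.
- For d = 1.0: 2 × 10.51 = 21.0, so 22 per arm. WOMAC pain drives the size. With 33 per arm, power for KAM impulse at 1.0 is 98.2% before any gain from the baseline covariate.

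**How far the speed-adjusted estimate could move**

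The documents give no speed data, so these inputs are assumptions: a baseline to follow-up correlation of 0.6 for outcome and for speed; a same-visit speed-outcome correlation ρ of 0.3 or 0.5; a cross-visit correlation of 0.6ρ; and a between-group speed shift of 0.25 or 0.5 SD.

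Slope of outcome on speed, given baseline outcome = (ρ − 0.6 × 0.6ρ) / (1 − (0.6ρ)²) = 0.64ρ / (1 − 0.36ρ²).

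- ρ = 0.3: 0.192 / 0.9676 = 0.198
- ρ = 0.5: 0.320 / 0.910 = 0.352

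Movement of the estimate = speed shift × slope. Simulation used 33 per arm, zero total effect and 8,000 trials per setting:

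| Speed shift (SD) | ρ | Movement (SD) | Speed-adjusted model rejects | Models disagree |
|---|---|---|---|---|
| 0.25 | 0.3 | 0.25 × 0.198 = 0.050 | 5.8% | 3.5% |
| 0.5 | 0.3 | 0.5 × 0.198 = 0.099 | 7.9% | 6.7% |
| 0.25 | 0.5 | 0.25 × 0.352 = 0.088 | 8.2% | 7.1% |
| 0.5 | 0.5 | 0.5 × 0.352 = 0.176 | 15.9% | 15.1% |

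- The baseline-adjusted ANCOVA rejects in 4.8% to 5.2% throughout.
- With no speed shift, neither model is biased (each rejects in 5.0% to 5.4%), and at least one rejects in 6.3% (ρ = 0.3) or 7.3% (ρ = 0.5).
- With ρ = 0 and a 0.5 SD shift, the estimate does not move and rejection is 5.1%.
- With a 0.1 SD shift, the movement is 0.1 × 0.198 = 0.020 to 0.1 × 0.352 = 0.035 SD.
- At a total effect of 1.0, both models reject in at least 99% of trials. They disagree in under 1%; a repeat run gave 0.2% to 1.1%.
- At a total effect of 0.5 SD, they disagree in 10% to 31% with a speed shift and 8% to 13% without one.

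**Sensitivity to the set-up**

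A second simulation left out the baseline outcome and used slopes of 0.3 to 0.5 in absolute size with speed shifts of 0.3 to 0.5 SD in either direction. Movement was about 0.3 × 0.3 = 0.09 to 0.5 × 0.5 = 0.25 SD. With no total effect, the speed-adjusted model rejected in 7% to 21% of trials. Disagreement was 14% to 41% at a total effect of 0.5, 7% to 20% at 0.8, and 1% to 7% at 1.0. These rates are less favourable partly because the residual SD is larger: a baseline correlation of 0.6 would cut it to √(1 − 0.36) = 0.8. When an unmeasured common cause offset the slope, the movement fell to about 0.01 to 0.03 SD.

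**The case for a change.** The strongest case for a change is that the hierarchy is inferred. The authors labelled their missing-data analyses and left these unlabelled; the sentence on group effects does not name a model; and at a moderate true effect the two models can disagree quite often, even with no effect on speed. Writing the hierarchy down would cost a sentence or two.

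The facts in that case stand: the label is absent, and the arithmetic is sound under its assumptions. What it does not show is that following the plan leads to a wrong primary result.

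- The proposed remedy keeps every analysis and only puts into words the order that the text already implies.
- Disagreement between a main model and an additional one is not an error in the main model.
- The larger figures need a between-group speed difference, and the design gives some reason to expect a modest one: both arms share the walking target, the trainer, and the treadmill and mirror sessions apart from the toe-out work. That does not exclude a difference.
- The rejection rates are not rates of false claims for toe-out. In the most extreme setting, a repeat run gave 14.4% rejections, of which 14.2 points lay on one side. Whether that side favours toe-out depends on signs that the documents do not give.
- For foot progression angle there is no stated link to speed, so the concern there reduces to a second p-value.

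Adjusting for Week 0 speed instead would avoid the post-randomisation problem. However, it is only a preference for precision, and it depends on data that the variable list does not name, although biomechanical data were collected at that visit.

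**Conclusion.** No change is needed. The plan adds models with a post-randomisation covariate and omits a formal label. Even so, the order of presentation, the wording, the coverage of all outcomes and the sample-size basis together identify the baseline-adjusted ANCOVA as the analysis that carries the primary conclusion. Its estimate, the sample size and the power are untouched by the speed models. For variables measured at self-selected speed, asking whether a difference persists at equal speed is a reasonable second question.

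The possible divergence is 0.05 to 0.18 SD for KAM impulse, which is 5% to 18% of the planned effect of 1.0 (up to 0.25 SD in the simpler set-up). It rests wholly on an assumed speed shift and correlation, is zero if either link is absent, and has an unknown direction. At the planned effect it would rarely change the verdict. An analyst reading the section as written would report the baseline-adjusted result as the trial's answer and the speed-adjusted one as supportive; stating this would be optional tidying.

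### The primary analysis reads as an observed-case ANCOVA at each visit under MCAR; this leaves mainly the retention contrast, not the primary follow-up contrast, open to a small avoidable bias

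*Combined protocol and SAP*

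**What the plan says.** The Statistical analysis section names follow-up as the primary endpoint. ANCOVA "models were fit predicting each outcome variable evaluated at both time points (follow-up and retention"), with group as predictor and the baseline value as covariate. For the biomechanical outcomes, extra models add gait speed measured at the same visit. On missing data: "All data were analyzed using an intention-to-treat analysis, and the primary analyses assumed that data were missing completely at random (MCAR"). Multiple imputation by a cited method is a sensitivity analysis; its results and conclusions are set against the MCAR analysis and differences are noted. The section does not list the imputation variables or the number of imputations, and does not say what follows if the two analyses disagree.

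On visits, the Study Design section says: "Follow-up testing occurred four months after baseline testing, with a final retention testing session conducted one month later". The same measures are taken each time. On expected loss, the sample-size paragraph under Participants says: "Using a conservative estimate of 10% attrition, the aim was to recruit 73 participants for this study".

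**The concern.** Neither the term complete case nor the term separate models appears in the plan. However, an ANCOVA at each visit, a gait-speed covariate tied to that visit, and an MCAR assumption with no imputation together point to one observed-case model per visit. Two things follow.

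First, anyone without that visit's value contributes nothing to that visit's estimate, so the analysed set is smaller than the randomised set that the intention-to-treat label suggests.

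Second, data in hand are left out. The follow-up score, taken one month before retention, plausibly predicts both who returns and what they score, yet the retention model omits it. Likewise, someone who misses follow-up but attends retention is lost from the primary comparison although a closely related score exists.

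If toe-out participants still in pain at follow-up return less often, the retention comparison would tilt towards toe-out.

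**Working it through.** **The plan's own figure.** The stated inputs are power and alpha ("required to attain 90% power to detect significant differences in pain and KAM outcomes between groups with an alpha of 0.05") and effect sizes ("Using effect size estimates of 0.8 for WOMAC pain and 1.0 for KAM impulse"). Two-sided testing and 1:1 allocation are assumed.

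- Pain: n per group = 2(1.960 + 1.282)²/0.8² = 2 × 10.51/0.64 = 32.8, so 33 per group and 66 in total.
- Attrition: 66 × 1.10 = 72.6, so 73; or 66/0.90 = 73.3, so 74. The stated 73 is reproduced.
- KAM impulse: 2 × 10.51/1.0² = 21.02, so 22 per group. Pain drives the sample size.
- With 10% missing, 73 × 0.90/2 = 32.85 per arm. Power = Φ(0.8 × √(32.85/2) − 1.960) = Φ(1.28) = 90.0%.

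The target therefore already pays for the lost precision at the planned attrition. What remains is bias.

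**Scale.** Assume SD 1 and correlation 0.5 between baseline and each later visit. The standard error at 10% missing is √[(1 − 0.5²) × 2/32.85] = √0.0457 = 0.214 SD.

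**Mechanism.** Let ρ be the follow-up to retention correlation. Given baseline, the slope of retention on follow-up is β = (ρ − 0.25)/0.75, which is 0.47, 0.67 and 0.80 for ρ = 0.60, 0.75 and 0.85. The retention ANCOVA bias is roughly β × Δ. Here Δ is the between-arm difference, among those who return, in mean follow-up score relative to what baseline predicts.

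- If loss depends only on arm and baseline, Δ = 0 and there is no bias, provided the linear model holds.
- To reach 0.08 SD at β = 0.80, Δ must be 0.08/0.80 = 0.10 SD. If 10% of one arm is lost, those lost must average 0.10 × 0.90/0.10 = 0.90 SD worse than baseline predicted. That is about four people (0.10 × 36.5 = 3.65).

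**Retention, simulated.** The assumptions are no true effect, 37/36 randomised, ρ = 0.60-0.85, and log-odds of loss changing by 0.75-1.5 per SD of follow-up pain where loss is pain-driven.

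| Loss pattern at retention | Bias in ANCOVA (SD) | Type I error |
|---|---|---|
| 10% in each arm, same dependence on pain | at most 0.01 | 4.4-5.2% |
| 10% in each arm, pain-driven in toe-out only | 0.02-0.08 | 5.2-6.7% |
| About 15% pain-driven in toe-out, 5% random in walking | 0.04-0.11 | 5.6-7.4% |
| Arms lose opposite ends, 13% missing, ρ = 0.75 | 0.16 | 11% |

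A joint estimator using both later visits had bias of at most 0.005 SD in the last two rows. The three-visit repeated-measures model recommended here was simulated at n = 73, about 10% missing, ρ = 0.75, with pain-driven loss in toe-out only. Its bias was under 0.01 SD, with no loss of precision.

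With a true effect of −0.8 SD, ρ = 0.7 or 0.8 and log-odds slopes of 1 or 2, ANCOVA bias at retention was 0.02-0.16 SD in size at 10% missing and 0.04-0.30 SD at 20%. The direction is not fixed. With the same pain dependence in both arms, ρ = 0.8 and 10% missing, the bias was 0.027-0.067 SD towards no difference, because the arms then differ in follow-up pain.

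**Follow-up (primary), simulated with the −0.8 SD effect.**

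- Drop-out driven by baseline pain, in the same or opposite direction by arm: bias within 0.005 SD.
- Missing follow-up but attending retention, with missingness in toe-out tracking the retention score: −0.03 to −0.07 SD at 10% and −0.06 to −0.12 SD at 20%. The joint model removes it.
- Drop-out on unseen follow-up pain with no later visit: 0.04-0.10 SD in size at 10%, identical under both models.

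**The case against.** The strongest reply is that the primary result is safe and the rest is already covered. Several parts of it stand.

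- **The primary contrast.** A reader might infer that the main pain result is biased whenever drop-out follows recorded pain. The documents do not support that. The only earlier testing-session score is baseline, which is already in the model.
- **The patterns needed.** Nothing in the documents suggests that loss differs by arm. The only figure is 10% overall attrition, called conservative. The 0.11 SD figure needs about three times the loss in toe-out as in walking, and 0.16 SD needs opposite-end loss.
- **The follow-up route.** It needs people to skip the primary visit, return a month later, and have missingness related to that later score. This is possible but narrow. If 10% miss follow-up at random and attend retention, the gain is only an SD of 0.211 instead of 0.217.
- **Intention-to-treat.** A reader might call the label false. That is too strong: the same sentence discloses the missing-data assumption, and analysis by randomised group is not in doubt. The label is incompletely met.
- **Multiple imputation.** It is planned and compared with the primary result. A reader might infer that it ignores the other visit. The plan points to a cited source and does not say, so that cannot be claimed.

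The reply does not explain why the headline estimate should carry the stronger assumption and leave out scores already collected, with the more tolerant analysis left to a check whose model is not described.

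**Conclusion.** The point holds in limited form. On its natural reading the primary analysis is observed-case at each visit under MCAR, despite the intention-to-treat label, and does not use the other post-baseline score. The primary follow-up contrast is unaffected by monotone drop-out that depends on arm and baseline.

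The exposure is mainly at retention, a non-primary time point. In the equal-loss and 15% versus 5% patterns the bias is at most about half a standard error (0.11/0.21 = 0.52); opposite-end loss raises this to about three quarters (0.16/0.21 = 0.76). The exposure at follow-up through intermittent attendance is smaller.

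All bias sizes rest on assumed SDs, correlations and missingness, because the documents give none. They were worked for pain; KAM impulse and foot progression angle were not sized separately. This is a cheap improvement worth making, not a defect that undermines the primary endpoint.

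**What to change.** In the Statistical analysis section:

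- For each outcome, fit one likelihood-based repeated-measures model with baseline, follow-up and retention as responses, a common baseline mean, group-by-visit effects and an unstructured covariance. Include all randomised participants and state the assumption as missing at random.
- Keep the follow-up group effect as the primary endpoint.
- Keep the visit-wise ANCOVA, labelled as a complete-case check, and use it for the gait-speed-adjusted models, which do not carry over simply once baseline is a response.
- Run the planned multiple imputation with all three visits in the imputation model, and list its variables and the number of imputations.

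The cost is SAP wording and a little programming in the SAS already named, with no new data and no change to the target of 73. Three visits need six covariance parameters, a modest burden at this size; a small-sample degrees-of-freedom correction is advisable. With complete data the follow-up result is almost unchanged. The change does not address drop-out that depends on unseen scores.
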